The LHA will meet with eligible patients and available caregivers in the intervention arm and assist them in watching the developed DVD segments. Afterward, the LHA will answer questions and provide additional information. They will tailor the discussion to the patient's values, preferences, concerns, and clinical circumstances. The patients who are enrolled in the usual care arm will not receive the intervention.

The primary process outcome tested will be the feasibility and acceptability of the intervention. Feasibility success will be measured by the number and rates of patients/caregivers who complete the intervention and follow-up interviews. The primary decision-making outcome is change in intent to discuss EOL care options based on the Transtheoretical Stages of Change Model (i.e., pre-contemplation, contemplation, preparation, and action). Secondary outcomes measured will include: 1) knowledge of prognosis and EOL care options; 2) quality of life, which will be measured by the McGill QOL Questionnaire, a well-validated 20 item scale developed to measure quality of life at the end of life; 3) health care utilization, such as outpatient visits, ER visits, hospitalizations, use of hospice services; and 4) date and place of death if applicable. Other patient and treatment variables will also be collected. The study variables, data sources, time frame of measurement, and references for the validated instruments are outlined in Table 2.

Table 2. Study Variables, Data Sources, and Time Frame Measurements

Variable	Source	Index Admit	Time Frame		
			1 month	3 months	6 months
Sociodemographics, clinical, treatment data	Chart review	X			
Knowledge of prognosis, EOL care options	Interview	X	X	X	
Feasibility and acceptability of the intervention	Interview	X	X	X	
Mistrust and spirituality	Interview	X	X	X	
Intent to consider EOL care options	Interview	X	X	X	X
Quality of life	Interview	X	X	X	
Healthcare and EOL utilization	Interview, chart	X	X	X	X

4. Study Procedures:

For Aim 1:

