The PI will use descriptive statistics to characterize study participants and proportion of intervention elements and follow-up assessments completed. The specificity and positive predictive value of the e-EOL algorithm operating in real world practice will be assessed using methods described for Aim 1 with physician chart review as the criterion standard. Acceptability and feasibility process data will be tallied. The main decision making outcome will be *change in the stage of intent to discuss EOL care options* from baseline through all follow-up intervals. Movement to an adjacent stage is a 1 point change. The PI will assess several aspects of stage change based on the proportion of patients at each time interval showing: 1) *any stage pro/regression*, and 2) *full progression to the action stage of discussion EOL care options*. Mean and range of progression at each interval will also be reported. The proportions above and means for *persistent change* will also be defined as the difference between baseline and 6 months (or 3 months if no 6 month contact or patient deceased). The PI will similarly examine pre- and post-intervention changes over time in knowledge, attitudes, and beliefs about EOL care and prognosis, decisional conflict, and QOL using non-parametric tests among the intervention group versus controls. Pre-specified subgroup analyses will stratify change in outcomes by: condition, mistrust, and spirituality. To achieve sensitivity of around 50% (with 10% confidence intervals, e.g. CI: 40% to 60%) in the outpatient algorithm, the PI will need to review 150 charts of patients diagnosed with metastatic (Stage III or IV) breast, lung and colorectal cancer (75 "test positive" and 75 "test negative" cases). The controlled pilot study in Aim 3 is designed to establish: feasibility, acceptability, detect preliminary efficacy signals (changes in behavioral intent, knowledge, attitudes, beliefs, decisional conflict), and generate point/variance estimates to be used to in power calculations for a future fully-powered RCT. The PI proposes a small pilot RCT that will include 24 patient-caregiver pairs in each arm (intervention versus a usual care control group). This will yield greater than 80% power to detect a large intervention effect defined as an absolute difference in desired primary outcome of 40% (across a range of different point estimates), and between 60-70% power to detect a more modest absolute difference of 30% between the two groups (across a range of point estimates). To ensure the ability to recruit the additional patient-caregiver pairs for the study, the PI will extend the enrollment period from 15 months to 18 months. Parkland Hospital providers care for more than 900 breast, lung and colon cancer patients per year, and roughly 40% are African American; consequently the PI believes that she will be able to successfully enroll this number of participants within an 18-month timeframe.

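### Stage of intent is summarised by raw change and by proportions of all patients: separate progression from regression, count progression only among patients below action at baseline, and compare stage within baseline-stage strata

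*Combined protocol and SAP*

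**What the plan says.** Section 3 (Concise Summary of Project, Aim 2) has two kinds of primary outcome. Feasibility and acceptability form the process outcome. For decision-making, "The primary decision-making outcome is change in intent to discuss EOL care options based on the Transtheoretical Stages of Change Model", with four stages: pre-contemplation, contemplation, preparation and action. Table 2 collects intent at the index admission and at 1, 3 and 6 months.

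The Statistical Analysis Plan scores a move to the next stage as one point. It then says "The PI will assess several aspects of stage change based on the proportion of patients at each time interval showing" two things: "any stage pro/regression", and full progression to action. Next comes "Mean and range of progression at each interval will also be reported". The proportions and means are repeated for persistent change, "defined as the difference between baseline and 6 months (or 3 months if no 6 month contact or patient deceased".

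The only named type of test, "using non-parametric tests among the intervention group versus controls", stands in the following sentence, on knowledge, attitudes, beliefs, decisional conflict and quality of life. The planned strata are condition, mistrust and spirituality, not baseline stage. The power statement, for 24 per arm, claims more than 80% for "an absolute difference in desired primary outcome of 40% (across a range of different point estimates"), and 60-70% for a 30-point difference. One stated aim is to "generate point/variance estimates to be used to in power calculations for a future fully-powered RCT".

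**The concern.** Three features of these summaries make them less informative than the collected data allow.

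1. **Ceiling.** A patient at action on admission cannot progress. Kept in the denominator, such patients shrink any between-arm difference in progression by the fraction of them present.
2. **Pooled direction.** A proportion with any movement counts a step forward and a step back alike. An intervention that raises progression and lowers regression changes the two parts in opposite directions, and the pooled figure can hide it.
3. **Baseline stage unused.** How far a patient can move depends on where the patient starts. Raw change ignores this; a comparison within baseline strata does not.

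At stake are the preliminary efficacy signal and the estimates that will size the next trial. A diluted difference carried forward would misstate the effect among patients who can still move.

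**Working it through.** **Inputs from the documents:** 24 per arm; differences of 40 and 30 points; four stages; intent recorded at index admission. **Assumed, because the documents give none:** two-sided 5% level, control rates of 10-50%, the baseline stage distribution, and the transition rates.

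**Step 1. The plan's own figures.** Exact power is the sum, over all pairs of counts (x, y) that the test rejects, of Bin(x; 24, p) × Bin(y; 24, p + d).

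| Test | d = 40 points | d = 30 points |
|---|---|---|
| Uncorrected chi-square | 84-90% | 59-71% |
| Fisher, two-sided | 75-83% | 47-60% |

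The stated figures reproduce under uncorrected chi-square. They do not hold throughout under Fisher.

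**Step 2. The ceiling.** Let a be the fraction at action at baseline and d the difference among the others. If patients at action are counted as not progressing, the overall difference is (1 - a) × d; for a = 0.20 it is 0.80 × 40 = 32 points. The all-patient analysis keeps 24 per arm with both rates multiplied by (1 - a). The restricted analysis has about 24 × (1 - a) per arm with the undiluted rates.

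| At action at baseline | Overall difference | Below action, per arm | Chi-square power, all patients | Chi-square power, below action |
|---|---|---|---|---|
| 10% | 36 | 22 | 75-85% | 78-86% |
| 15% | 34 | 20 | 70-82% | 71-84% |
| 20% | 32 | 19 | 65-79% | 72-82% |
| 30% | 28 | 17 | 53-72% | 69-75% |

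The smaller denominator costs less than the dilution. In 42 simulated settings, restricting the denominator gained 1-10 points in every one.

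**Step 3. Pooling.** Take a baseline of 40/30/15/15% across the four stages. Then 85% can progress and 60% can regress.

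- *Progression 60 v 25% and regression 5 v 15% among those able to move.* Progression overall is 0.85 × 60 = 51.0% v 0.85 × 25 = 21.3%, a difference of 29.8 points. Regression is 0.60 × 5 = 3% v 0.60 × 15 = 9%. Pooled: 54.0% v 30.3%, a difference of 23.8 points.
- *Progression 50 v 25% and regression 5 v 25%.* Progression is 42.5% v 21.3%, a difference of 21.3 points. Regression is 3% v 15%. Pooled: 45.5% v 36.3%, a difference of only 9.3 points.

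In the second case pooling removes more than half of the difference, although both components favour the intervention. In simulations with a proportional effect and this baseline mix, the pooled proportion had only 8-18% power.

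**Step 4. Using baseline stage.** The simulations had 24 per arm, complete follow-up, 10,000 trials per setting, and critical values calibrated to 5% null rejection. They compared a Wilcoxon test stratified by baseline stage with a Wilcoxon test on raw change.

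| Effect pattern | Raw change | Stratified | Gain, points |
|---|---|---|---|
| Proportional, odds ratio 4.5 | 59-68% | 68-75% | not listed by setting |
| Proportional, odds ratio 2.7 | 32-37% | 34-42% | not listed by setting |
| 18 transition settings, not built on that model | not listed | not listed | -2 to +3 |

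Over all 42 settings the gain ran from -2 to +14 points. In five settings with the baseline mix of step 3 and stages missing at random, it was -1 to +9 points with 20% missing and -1 to +6 with 40% missing. In the six settings where the arms differ only in progression, the simple progression proportion beat the stratified test by 7-12 points (uncalibrated).

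**The case against.** The strongest reply is that this is a feasibility pilot. The plan says that it will assess and report these summaries; it does not promise a confirmatory test of each. Describing several candidate endpoints so that the next trial can choose is legitimate. That stands, and it limits the weight of the point.

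The gain from stratifying is also uncertain. It is measured against a Wilcoxon test on raw change, which the plan does not clearly name for stage. It nearly vanishes in settings not built on a proportional effect, and a plain proportion can win. This stands too, so step 4 is offered as a modest refinement. The denominator and the split of directions do not depend on it.

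The pro/regression wording may already intend separate reporting, since the one-point scoring and the mean suggest that direction is kept. That is plausible, but the text does not say so.

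A reader might infer more than the documents support:

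- *That the power figures are wrong.* They reproduce under uncorrected chi-square. Fisher's lower power reflects its conservatism: its null rejection is only about 2-3% at this size. Naming the proportion and the test is a clarification.
- *That three summaries at four occasions (3 × 4 = 12), none ranked, create a false-positive problem.* The plan does not say that it will test all twelve, and persistent change equals the 6-month value wherever that contact exists.
- *That a proportional-odds model would bring a large gain.* Its largest gains, up to 17 points, arise where the data were generated from that very model; elsewhere they were -1 to +7. Its likelihood-ratio test also rejected up to 7.1% under no effect.
- *That baseline stage is recorded after the DVD.* Section 4 mentions noting stage only after it describes the DVD and counselling. But Table 2 marks intent at index admission, the analysis plan speaks of baseline, and all participants are asked, including controls who see no DVD.

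**Conclusion.** The point holds in a limited form. As written, the summaries dilute progression by the share of patients already at action and may pool opposite movements, and they use baseline stage only by subtraction. With an assumed 20% at action, a 40-point effect becomes 32 points, and chi-square power is 65-79% on all patients against 72-82% below action. Pooling can cost more than half of a real difference under the assumed transition rates. Stratifying adds roughly nothing to a few points in transition settings, and more if the effect is proportional.

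The dilution formula is arithmetic once the share at action is known. That share, the transition rates and the effect patterns are all assumptions. Nothing here affects feasibility or acceptability, or shows the stated power to be false. It is a worthwhile refinement of low to moderate importance.

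**What to change.** In the Statistical Analysis Plan:

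1. Report progression and regression as two separate proportions.
2. Compute progression and movement to action among patients below action at baseline, and give the number at action in each arm.
3. For the between-arm comparison of stage, use a Wilcoxon test stratified by baseline stage at one time point of the sponsor's choice. State that baseline is the value recorded before the DVD is shown. Label the other summaries and time points supportive.
4. As a clarification, name the proportion and the test behind the 40- and 30-point power figures.

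The cost is a few sentences and a few lines of code; no new data are needed. The downsides are a slightly smaller denominator for progression, and some loss of power for the stratified test against a simple progression proportion if the intervention affects progression alone.

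### For the secondary scales the SAP names only non-parametric tests of change and commits to no SD, confidence interval or baseline-adjusted difference

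*Combined protocol and SAP*

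**What the plan says.** The Statistical Analysis Plan section deals with the secondary scales in one sentence. It opens "The PI will similarly examine pre- and post-intervention changes over time in knowledge, attitudes, and beliefs", goes on to decisional conflict and QOL, and ends "using non-parametric tests among the intervention group versus controls". The test is not named. No between-arm estimate, SD, confidence interval, baseline adjustment or longitudinal model is mentioned for these scales.

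The word *similarly* points back to the stage-of-intent outcome. The summaries given there are proportions, means for persistent change, and this: "Mean and range of progression at each interval will also be reported".

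The same section says the pilot "is designed to establish: feasibility, acceptability, detect preliminary efficacy signals", and that it will "generate point/variance estimates to be used to in power calculations for a future fully-powered RCT". Section 3 (Aim 2) adds "The primary process outcome tested will be the feasibility and acceptability of the intervention", and lists among the secondary outcomes "quality of life, which will be measured by the McGill QOL Questionnaire, a well-validated 20 item scale". Table 2 schedules knowledge and quality of life at the index admission, 1 month and 3 months. Decisional conflict has no row in Table 2.

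**The concern.** A later trial that uses one of these scales needs an SD, a plausible between-arm difference with its uncertainty and, if it will adjust for baseline, the index-to-follow-up correlation. A test result supplies none of these. Means and ranges, if they carry over through *similarly*, supply a point estimate but not a variance. For these scales, then, one stated purpose of the pilot has no analysis assigned to it.

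The second issue is precision. The quantity described is change from before to after the intervention, with no adjustment named. Subtracting the index value carries all of its measurement noise into the comparison, whereas using it as a covariate removes only the part that predicts follow-up. With at most 48 patients, fewer after deaths and missed calls, the difference can matter.

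**Working it through.** **The plan's own figures.** No power or precision is stated for the secondary scales. The stated power concerns a difference in proportions on the primary decision-making outcome, with 24 per arm. Taking two-sided 5% and the pooled normal approximation (neither is stated), a 40-point difference has 81.2% to 91.9% power across control rates 0.05 to 0.55, which agrees with the stated figure of more than 80%. A 30-point difference has 54.9% to 75.4% across control rates 0.05 to 0.65, against a stated 60-70%. Neither figure bears on this point.

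**Inputs.** 24 per arm is from the SAP. The index-to-follow-up correlation r is not in the documents, so 0.3 to 0.8 is assumed. Variances are taken as equal at index and follow-up, in units of the index SD, with no dropout.

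**Variance of the between-arm difference.**

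- Change score: 2(1−r) × 2/24.
- Adjusted for the index value: (1−r²) × 2/24.
- Ratio, adjusted to change: (1−r²) / [2(1−r)] = (1+r)/2.

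| r | SE, change | SE, adjusted | Variance ratio | 24 per arm on change is worth, per arm when adjusted |
|---|---|---|---|---|
| 0.3 | 0.342 | 0.275 | 65% | 15.6 |
| 0.5 | 0.289 | 0.250 | 75% | 18.0 |
| 0.7 | 0.224 | 0.206 | 85% | 20.4 |
| 0.8 | 0.183 | 0.173 | 90% | 21.6 |

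The direction does not need equal variances. With index SD s0 and follow-up SD s1, the change-score variance minus the adjusted variance is (s0² + s1² − 2r·s0·s1) − s1²(1−r²) = (s0 − r·s1)², which is never negative. Estimating the slope raises the adjusted variance by about 1/(48−4) = 1/44, or 2%. That leaves the advantage in place over the range shown.

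**Which step costs the precision.** The efficiency of the rank test relative to the t-test under normality is 3/π = 0.955, a loss of about 5%. Simulated power (4,000 trials per setting, normal data, an assumed true difference of 0.8 SD, 24 per arm):

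| r | Mann-Whitney on change | t-test on change | ANCOVA |
|---|---|---|---|
| 0.3 | 60% | 64% | 80% |
| 0.5 | 73% | 76% | 86% |
| 0.7 | 92% | 94% | 96% |

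A separate run of the same size agreed within about 2 points. It gave rank ANCOVA 79%, 84% and 95%, against 82%, 87% and 96% for ordinary ANCOVA. Nearly all the loss therefore comes from using unadjusted change. With 18 evaluable per arm, Mann-Whitney on change had 48%, 61% and 83%, and ANCOVA 68%, 76% and 90%.

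**Why the SD needs an interval.** An SD pooled over two arms of 24 (46 degrees of freedom) has a 95% CI of 0.83 to 1.26 times the estimate. Sample size scales with the square, so the implied range is 0.83² = 0.69 to 1.26² = 1.59 times the planned size.

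**The case against.** The SAP sentence is short, and much can be read into it. A reader might infer four things that the documents do not support.

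- *That the SAP prescribes rank tests of change, one per interval.* It says only that the tests are non-parametric and the changes are over time. Rank ANCOVA or a non-parametric longitudinal method would also fit.
- *That the analysis will yield p-values and nothing else.* Means plausibly carry over through *similarly*, and a rank test can be paired with a Hodges-Lehmann estimate and interval. The SAP does not exclude these; it does not commit to them.
- *That the pilot exists to produce these estimates.* Feasibility and acceptability come first and are the primary process outcome. The future trial is described in section 1 as aimed at intent to discuss end-of-life care, so stage proportions are its natural planning input, and a variance follows from them. Quality of life is not among the efficacy signals the SAP lists; knowledge, attitudes, beliefs and decisional conflict are.
- *That the non-parametric choice is the error.* Ranking is cheap under normality and can gain on skewed or bounded scales.

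It is also fair to say that the size of the loss rests on an assumed r, that at r = 0.7 the power gap is small, and that no power claim in the SAP fails.

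All of this stands, and it limits the point. It does not remove it: on the most generous reading, the plan offers means and ranges for these scales, and a range is not a variance.

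**Conclusion.** The point holds in a limited form. For the secondary scales the SAP names a class of test and commits to no SD, confidence interval or baseline-adjusted difference, although point and variance estimates for a later trial are one of its stated purposes. Comparing unadjusted change would also give away precision: the adjusted estimate has 65%, 75% or 85% of the change-score variance at r = 0.3, 0.5 or 0.7. Those ratios assume equal variances and a correlation that the documents do not give. The power figures further assume normal data and a 0.8 SD difference. This is a worthwhile improvement to reporting and efficiency. It does not affect the feasibility and acceptability assessment or the staging of the primary decision-making outcome.

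**What to change.** Replace the sentence on the secondary scales with a commitment to report, for each scale at each visit where it is scheduled (1 and 3 months in Table 2 for knowledge and quality of life):

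- n, mean and SD by arm, with a 95% CI for the pooled SD;
- the index-to-follow-up correlation;
- the between-arm difference adjusted for the pre-intervention index value, with 95% CI.

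Use ANCOVA at each visit, or a mixed model over the scheduled visits, which keeps a patient who misses one call. Keep a non-parametric analysis, preferably rank ANCOVA on the index value, as a sensitivity analysis. State the visits for decisional conflict, which Table 2 omits. State also that the covariate is the value taken before the DVD is shown: section 4 names only knowledge for the patient pre-assessment interview, and mentions quality of life and decisional conflict in the counselling that follows the DVD.

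The cost is a few sentences and a little more analysis, with no new data provided each scale is measured before the intervention. The downsides are one degree of freedom for the covariate and a distributional assumption at n of at most 48, which the rank-based analysis checks. A mixed model treats values after death as missing, so deaths by arm should be reported beside it. The residual SD of a random-intercept model leaves out between-patient variance and would understate the SD needed for planning, so it cannot replace the raw SDs.

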Study Protocol and Statistical Analysis Plan

Protocol: Planning for the Care you Want
Rev. 9/18/2017

PI: [name]

NCT: 02320123

The University of Texas Southwestern Medical Center at Dallas
Institutional Review Board

[figure not shown]
Title: Planning for the Care You Want

Funding Source: AHRQ 1R24HS022418-01 (PI: [name]), Palliative Care Research Cooperative Group (PI: [name])

- 1. Introduction and Purpose:** The goal of this patient-centered project is to develop and pilot test a multicomponent intervention to increase intent to discuss end-of-life (EOL) care options among African American (AA) patients with life-limiting illness. This will be accomplished through the following specific aims, which are to: 1) Develop and refine a culturally sensitive intervention to increase knowledge about, reduce barriers, and promote intention to discuss EOL care options among AA patients hospitalized with advanced illness who are ≥ 55 years of age; and 2) Test the feasibility and acceptability of a theory-based, multi-component pilot program that will identify older AA patients hospitalized with advanced illness via the e-EOL algorithm and then deploy a culturally sensitive, patient-centered intervention to change knowledge and barriers about and intent to discuss EOL care options.

A separate aim is also included in the overall study, which has been funded by the Agency for Healthcare Research and Quality (AHRQ) and the Palliative Care Research Cooperative Group. The entire 3-aim study is Project 2 in the AHRQ-funded UT Southwestern Center of Patient-Centered Outcomes and Research. The first aim mentioned above, serves as a precursor to the aims described in this protocol. This aim, which uses applied medical informatics and chart review methods to develop an EMR-enabled (e-EOL) algorithm to identify patients hospitalized with advanced breast, lung, and colorectal cancer appropriate for EOL care counseling was approved in IRB submission STU 122010-078. It will be referred to at times in this protocol. Figure 1 shows the flow of the chronological flow of the entire proposal.

Figure 1

For the purposes of this IRB protocol, Aims 2 and 3 of the overall project will be referred to as Aim 1 and Aim 2 moving forward.

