B. A lay health advisor (LHA) will be recruited from the community to provide counsel about EOL care to patients who will receive the intervention. The LHA will undergo training in how to provide culturally sensitive EOL care for AAs via the APPEAL (A Progressive Palliative Care Educational Curriculum for the Care of AAs at Life's End) Curriculum created at Duke University, the Respecting Choices® Advance Care Planning curriculum, or other appropriate training program depending on availability. After training, the LHA will participate in in-service work with the Parkland Palliative Care Team and the PI.

Aim 2:

We will use the e-EOL algorithm (IRB #: STU 122010-078) to identify AA patients hospitalized at Parkland who have advanced breast, lung, and colorectal cancer to identify potentially eligible candidates for the intervention (See Aim 1 eligibility criteria); however, if sufficient numbers are not identified, patients with other advanced cancers will also be considered. Once eligibility is confirmed the PI or her designee (research assistant, coordinator, or LHA) will introduce the study to the patient, and obtain informed consent. Each patient will be asked to identify a primary caregiver who may be able to participate in the intervention. Of note, if a caregiver cannot be identified, is not eligible, or cannot participate in the intervention for other reasons (scheduling difficulties, etc.), the patient will still be allowed to participate. Caregivers are not required to participate in the intervention (i.e. watch the DVD segments), though it will be encouraged. The PI or her designee (research assistant, coordinator, or LHA) will contact the patient to confirm participation in the study, and arrange a time to meet to conduct the intervention. We anticipate that 48 patients (and their caregivers if available) will be enrolled in the study (16 for each type of cancer). We plan to conduct a small, pilot randomized controlled trial with up to 24 patients (and their caregivers if available) in the intervention arm, and up to 24 patients (and their caregivers if available) in a usual-care control group. The PI will randomize every other eligible patient (and caregiver if available) to the usual-care control group.

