9. Recruitment Methods and Consenting Process: Aim 1: The PI and research assistant will work with the attending physicians in the Parkland Palliative Care Clinic, Amelia Court Geriatrics Clinic, the Parkland inpatient Geriatrics and General Internal Medicine services, and researchers at the Simons Cancer Center to identify eligible candidates for semi-structured interviews and focus groups. Information will also be obtained for patient's caregivers, and they will be contacted by phone and regular mail to assess their interest in participation.

Palliative Care providers will be recruited via professional contacts. Providers will be approached via email and phone to assess their interest in participating in the focus group.

AA Religious leaders will be recruited from the African American Pastors Coalition and/or local AA churches. They will be approached by email (if available) and phone to assess their interest in participating in the study.

Aim 2: Patient participants will be recruited via development of a computerized algorithm using EMR data to identify hospitalized patients with advanced illness appropriate for EOL care discussion according to national guidelines. Development and validation of this algorithm is currently in process and has already received IRB approval (STU 122010-078: Evaluation of Racial Differences in Palliative and End-of-Life Care among Persons with Life-Limiting Illness). The algorithm will run once every day to flag potentially eligible candidates using an IT protocol used successfully in previous research at Parkland. The PI or her designee (research assistant or research coordinator) will contact the attending physicians of those identified by the algorithm to confirm eligibility and get permission to introduce the study to those patients. Creation of the algorithm is actually Aim 1 of an AHRQ-funded study that includes all three aims; consequently, the algorithm will be complete enough to use for recruitment in Aim 2 described here.

The PI or her designee (research assistant, research coordinator, or LHA) will contact each patient's primary caregiver by phone to confirm their participation in the study.

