12. Procedures to Maintain Confidentiality: No identifying information will be included in the transcription of the focus groups or on any instruments. The instruments will be coded and the master list that links the individual and the code will be maintained by a member of the research staff under lock and key or on a password-protected computer. At the end of the study, the recorded information and the document linking participant with his/her code will be destroyed.

13. Potential Benefits: The benefits to the human subjects identified in this research are as follows. They will receive information about options for care that they might otherwise not have known about. This will be done by a culturally sensitive EOL counselor with specific training in providing counsel to AA with chronic illnesses. There is also potential benefit to future patients requiring end-of-life care and to society. Data collected for this research will allow the PI and research team to identify persons from underrepresented groups who may not be aware of their options for EOL care, and consequently design multifaceted interventions to reduce previously identified disparities.

Study Title: Aim 1 (Development of the intervention)

Total Planned Enrollment: 68

TARGETED/PLANNED ENROLLMENT: Number of Subjects			
Ethnic Category	Sex/Gender		
	Females	Males	Total
Hispanic or Latino	0	0	0
Not Hispanic or Latino	34	34	68
Ethnic Category: Total of All Subjects *	34	34	68
Racial Categories			
American Indian/Alaska Native	0	0	0
Asian	0	0	0
Native Hawaiian or Other Pacific Islander	0	0	0
Black or African American**	26	26	52
White***	8	8	16
Racial Categories: Total of All Subjects *	34	34	68

** Patient/caregiver pairs, and AA religious leaders ***Palliative care Providers

Study Title: Aim 2 (Pilot test of the intervention)

Total Planned Enrollment: 96

TARGETED/PLANNED ENROLLMENT: Number of Subjects			
Ethnic Category	Sex/Gender		
	Females	Males	Total
Hispanic or Latino	0	0	0
Not Hispanic or Latino	48	48	96
Ethnic Category: Total of All Subjects *	48	48	96
Racial Categories			
American Indian/Alaska Native	0	0	0
Asian	0	0	0
Native Hawaiian or Other Pacific Islander	0	0	0
Black or African American	48	48	96
White	0	0	0
Racial Categories: Total of All Subjects *	48	48	96

Statistical Analysis Plan:

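### Does the Statistical Analysis Plan size its chart review for the wrong algorithm and point to the wrong aim for its accuracy methods?

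*Combined protocol and SAP*

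**What the plan says.** The Statistical Analysis Plan makes two statements about algorithm accuracy.

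- On measures and method: "The specificity and positive predictive value of the e-EOL algorithm operating in real world practice will be assessed using methods described for Aim 1". The reference against which the algorithm is judged is a physician's reading of the chart.
- On size: "To achieve sensitivity of around 50% (with 10% confidence intervals, e.g. CI: 40% to 60%) in the outpatient algorithm", 150 charts are to be reviewed, 75 test positive and 75 test negative, from patients with Stage III or IV breast, lung or colorectal cancer.

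It then describes the randomized pilot: "The controlled pilot study in Aim 3 is designed to establish" feasibility, acceptability and early signals of effect.

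Elsewhere the algorithm has an inpatient setting. Section 1 speaks of an "algorithm to identify patients hospitalized with advanced breast, lung, and colorectal cancer appropriate for EOL care counseling". Section 3, under Aim 2, uses it to "identify AA patients hospitalized at Parkland who have advanced breast, lung, and colorectal cancer". Section 9 describes a "computerized algorithm using EMR data to identify hospitalized patients with advanced illness appropriate for EOL care discussion".

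On numbering, Section 1 says that "Aims 2 and 3 of the overall project will be referred to as Aim 1 and Aim 2 moving forward". The enrollment table just before the Statistical Analysis Plan is headed "Study Title: Aim 1 (Development of the intervention".

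**The concern.** A reader who applies the protocol's own numbering goes to Aim 1 for the specificity and predictive-value methods. There they find DVD segments, interviews, focus groups and training of the lay health advisor, but no chart review and no accuracy estimate.

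The same reader sees the only chart-review sample size attached to an outpatient algorithm, although the pilot recruits through an algorithm for inpatients. The stated precision is for sensitivity, while the measures promised for real-world use are specificity and positive predictive value.

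If these were errors of substance, the accuracy results would have no traceable method, and the 150 charts might say nothing about the tool that recruits the pilot's patients.

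**Working it through.** **Which numbering does the Statistical Analysis Plan use?**

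| Work | Overall project | This protocol (Section 1) | Statistical Analysis Plan |
|---|---|---|---|
| e-EOL algorithm | Aim 1 | separate submission, STU 122010-078 | Aim 1 |
| Development of the intervention | Aim 2 | Aim 1 | not numbered |
| Randomized pilot | Aim 3 | Aim 2 | Aim 3 |

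This protocol has no Aim 3. The Statistical Analysis Plan therefore uses the overall-project numbers, and within them it is consistent. Section 9 states outright that creating the algorithm is Aim 1 of the three-aim project and gives the IRB number. Section 1 says that aim uses informatics and chart-review methods. The pointer leads to a protocol that is not reproduced here, but it can be followed.

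**Does the plan call the recruiting algorithm outpatient?** No. It names the e-EOL algorithm in one sentence and an outpatient algorithm in a later one, and does not equate them. The word may be a slip, or it may refer to another version developed under the separate submission. The documents do not settle which.

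**Is the figure of 150 wrong?** Inputs from the plan: sensitivity s = 0.50, half-width 0.10, 75 charts in each test group. Not given: the confidence level, the criterion-positive share p and the flag rate f. Both 95% and 90% confidence are tried below.

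1. *Simple proportion.* n = z² × 0.25 / 0.10². At 95%, 1.96² × 25 = 96.04, so 97 criterion-positive charts. At 90%, 1.645² × 25 = 67.6, so 68. Neither gives 150 directly. All 150 charts would contain 97 criterion-positive ones if 97/150 = 64.7% of them were criterion-positive.
2. *If 75 charts form the denominator.* Half-width = z × √(0.25/75): 1.96 × 0.0577 = 0.113 at 95% and 1.645 × 0.0577 = 0.095 at 90%. The stated 10 points lie between the two.
3. *If charts are sampled by algorithm result and reweighted by a known flag rate.* Half-width = z × s(1−s) × √{([f/s + (1−f)/(1−s)]/p − 2)/75}. At s = 0.50 the flag rate cancels, leaving z × 0.25 × √{(2/p − 2)/75}. Setting this to 0.10 gives p = 0.390 at 95% and 0.311 at 90%.

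Reading 3 over a range of p, at 95%:

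| Assumed p | Half-width (points) |
|---|---|
| 12.8% | 20.9 |
| 25.6% | 13.6 |
| 38.4% | 10.1 |
| 64.0% | 6.0 |

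The stated interval is attainable under some of these assumptions and not under others. The documents do not fix p, so 150 is neither confirmed nor refuted.

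**Does anything in the pilot depend on it?** The power statement uses 24 patient-caregiver pairs per arm and absolute differences of 40% and 30%; no sensitivity, specificity or flag rate enters. Algorithm accuracy is not among the primary or secondary outcomes in Section 3. Section 9 has the attending physicians confirm the eligibility of flagged patients, so the flag alone does not admit anyone.

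**The case for a change.** The strongest reply is that this document sets its own numbering and that the Statistical Analysis Plan cites neither the overall project nor the IRB number at the point of use. The accuracy methods are absent from these pages under either numbering.

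There is also a substantive edge. Recruitment as described in Section 9 follows up only flagged patients. Positive predictive value can be estimated from them; specificity also needs true negatives among the unflagged. The 75 test-negative charts could supply these only if they concern the inpatient algorithm, which is the very point left unclear.

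The textual part of this stands: the labels are out of step and the outpatient term is unexplained. The specificity part does not establish a defect. Whether unflagged patients are reviewed is a matter for the separately approved algorithm study, and these documents do not show that they are not. The plan does name the criterion standard, and both measures have standard definitions. An analyst would report the predictive value from flagged patients, and specificity only where unflagged charts had been read.

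**Conclusion.** No change to the plan follows. What remains is a clerical carry-over of aim numbers and one undefined term: one section says outpatient, three say hospitalized. The intended source of the methods can be traced through Sections 1 and 9. No stated rule or figure is shown to give a wrong result. The 40% to 60% interval fits a weighted 75:75 design if about 39% of patients are criterion-positive at 95% confidence, or about 31% at 90%; both shares are assumptions, conditional on a sensitivity of 50% and a known flag rate. The conclusion about the pilot needs none of these assumptions, because its size, power statement and outcomes take nothing from the chart review. The conclusion about the pointer rests on reading the Statistical Analysis Plan in the overall-project numbering, which its own use of Aim 3 supports.
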